1 INTRODUCTION AND BACKGROUND INFORMATION

Dyslipidemia is a collective term used to describe a spectrum of disorders in lipid metabolism arising from a combination of genetic, environmental, and pathological factors. It is characterized by elevations in serum total cholesterol, low-density lipoprotein (LDL) cholesterol (LDL-C) and triglyceride (TG) concentrations, and/or an attenuation of the high-density lipoprotein (HDL) cholesterol (HDL-C) fraction. Diagnosis is made by measurement of serum lipids and is classified by the pattern of elevation/reduction in the lipid/lipoprotein fractions, mode of inheritance (or lack thereof), and presence of clinical manifestations. Dyslipidemia can lead to symptomatic obstructive or occlusive atherosclerotic disease of various vascular arterial beds. Normalization of the lipid profile to guideline-mandated targets, therefore, is widely accepted as the cornerstone of cardiovascular (CV) protection strategies.¹

If lifestyle modification strategies alone prove inadequate, statins are generally the drug of first choice to treat dyslipidemia. Patients unable to achieve treatment goals with a maximally tolerated statin therapy require an additional lipid-lowering therapy such as ezetimibe. Those intolerant to statins or unable to achieve treatment goals with statin (± ezetimibe) may be offered bempedoic acid, an inhibitor of cholesterol synthesis by the liver, or modulators of proprotein convertase subtilisin kexin type 9 (PCSK9) function such as inclisiran, an interfering RNA that blocks translation of PCSK9 protein, or monoclonal antibodies that directly inhibit PCSK9, such as alirocumab and evolocumab.

However, there are several limitations with these lines of therapy, such as very high costs, availability restricted predominantly to specialist clinics, a paucity of long-term efficacy data relative to statins, and muscle-related events with PCSK9 inhibitors. Furthermore, because PCSK9 inhibitors are injectable, they pose a less attractive option for patients who prefer oral medications, and they have not received the expected utilization by clinicians or patients. The 2 non-statin oral LDL-C-lowering therapies, ezetimibe and bempedoic acid, have a modest effect on LDL-C reduction and, therefore, often do not provide the efficacy required for high-risk atherosclerotic cardiovascular disease (ASCVD) patients.

Above all, there remains an unmet medical need for therapies to reduce LDL-C levels and CV risk at an acceptable cost, in a convenient dosage form, and with a favorable tolerability and safety profile to maintain long-term lipid-lowering efficacy and patient adherence to therapy.

1.1 Cholesteryl Ester Transfer Protein Inhibitors

Cholesteryl ester transfer protein (CETP) is a plasma glycoprotein produced in the liver and adipose tissue. It circulates in the blood, bound primarily to HDL-C, and is involved in the transfer of cholesteryl esters and TG between lipoproteins. In particular, CETP mediates the transfer of cholesteryl esters from HDL to apolipoprotein B (ApoB)-containing particles, i.e., very low-density lipoprotein and LDL-C, in exchange for TG.

Inhibition of CETP activity reduces LDL-C levels and increases HDL-C. These effects are not only caused by inhibition of CETP-mediated cholesterol transfer from HDL to LDL, but also by a decrease in the number of ApoB-containing particles.^{2,3} The LDL-C lowering effect mediated by CETP inhibition is anticipated to benefit patients with elevated LDL-C and increased CV risk.

1.2 Obicetrapib

Obicetrapib is a highly selective and potent CETP inhibitor, which has been developed for the treatment of dyslipidemia and CV risk. It is a small molecule that blocks the transfer of cholesteryl ester from non-atherogenic HDL particles to particles in lipoprotein fractions (including LDL) that cause atherosclerosis and reduces the concentration of cholesterol not only in LDL, but also in other atherogenic lipoproteins. Moreover, obicetrapib treatment will not only reduce the number of ApoB-containing particles that constitute LDL-C, it can also upregulate the concentration of apolipoprotein E (ApoE), which results in the removal of cholesterol via the liver and also reduced lipoprotein (a) (Lp[a]). Finally, obicetrapib not only potently increases HDL-C and the concentration of apolipoprotein A1 (ApoA1)-containing lipoproteins but has also been shown to be a potent inducer of cholesterol efflux, which is the main driver of reverse cholesterol transport. This effect is considered important because it can lead to regression of established atheroma burden.

1.3 Clinical Development of Obicetrapib

Both single ascending dose (TA-8995-01) and multiple ascending dose (TA-8995-02) studies have been conducted in healthy volunteers. A formal and thorough QT/QTc study (TA-8995-04) of obicetrapib has been completed and demonstrated no adverse effect on QTcF prolongation. A drug-drug interaction study (TA-8995-05) has also shown no significant effect of obicetrapib on P-glycoprotein activity but did indicate that obicetrapib is a mild inducer of cytochrome P450 3A4. A mass balance study (TA-8995-07) in healthy males concluded that obicetrapib is steadily absorbed, and the principal route of excretion was in the feces. Furthermore, bioequivalence between obicetrapib capsule and tablet formulations (TA-8995-08) has previously been demonstrated.

A Phase 2 patient study (TA-8995-03) was conducted in Denmark and the Netherlands to evaluate the optimal dose of obicetrapib alone and in combination with medium-intensity statins in patients with mild dyslipidemia. A daily dose of 10 mg obicetrapib in combination with medium-intensity statins resulted in an incremental LDL-C reduction of up to 45.3% and a total LDL-C reduction of 68.2%, while statin monotherapy or obicetrapib monotherapy achieved a comparatively weaker LDL-C reduction of ≤45.4%. When compared with statin treatment alone at the end of the 12-week Treatment Period, all treatment groups with obicetrapib in combination with medium-intensity statins had significantly higher mean HDL-C levels; significantly greater increases in ApoA1 and ApoE levels; and a higher reduction in ApoB, Lp(a), and non-high-density lipoprotein cholesterol (non-HDL-C) levels.

Currently, Phase 3 studies are ongoing in which obicetrapib is added to a pre-existing maximally tolerated lipid-lowering therapy regime taken by participants with established sequelae of ASCVD.

Indeed, the Phase 2 study (TA-8995-03) of obicetrapib described above was conducted in Northern European, predominantly Caucasian participants. Thus, there is a lack of clinical experience with obicetrapib when used in combination with moderate intensity stable statin therapy among individuals from the Asia-Pacific region. Study TA-8995-203 is designed to fill the gap in clinical experience and characterize the safety, efficacy, and pharmacokinetics (PK) profile of obicetrapib within this population.

1.4 Rationale

This dose-finding, Phase 2, double-blind, randomized study of obicetrapib versus placebo aims to confirm the safety and efficacy of the active compound in Japanese participants.

1.5 Risk/Benefit

Obicetrapib has undergone extensive nonclinical testing according to the International Council for Harmonisation (ICH) guidelines, including repeat-dose toxicity studies of up to 39 weeks duration. In addition, obicetrapib has been investigated in 8 completed clinical studies, of which 6 studies were in Phase 1 of clinical development and 2 studies were in Phase 2. A total of approximately 500 participants have been exposed to obicetrapib in these studies. In Phase 1, a total of 159 participants received single oral doses between 5 and 150 mg of obicetrapib, and 76 participants received consecutive doses between 1 and 25 mg of obicetrapib for periods up to 28 days. In Phase 2, a total of 268 patients received 1 to 10 mg of obicetrapib for up to 12 weeks.

In healthy volunteer studies, single doses of obicetrapib up to 150 mg and multiple doses up to 25 mg/day over 28 days were generally well tolerated. Obicetrapib was also well tolerated after daily dosing of 10 mg for 12 weeks, both alone and in combination with 2 different statins. There were no dose-related adverse events (AEs) identified and no clinically significant changes in vital signs, 12-lead electrocardiograms (ECGs), hematology, or biochemistry in any clinical trials. Most treatment-emergent AEs (TEAEs) were mild or moderate in severity. None of the severe TEAEs were considered related to the study drug. The number of patients experiencing TEAEs and their severity were similar across all treatment groups. Incidence rates of drug-related TEAEs were also comparable for all treatment groups; the number of TEAEs in the obicetrapib treatment groups did not indicate a dose-dependent effect. There were 7 patients, who were randomized to receive obicetrapib alone or in combination with statin, with a treatment-emergent serious AE (SAE), none of which were suspected to be related to study drug. One patient had a treatment-emergent SAE that resulted in study discontinuation.

1.6 Coronavirus Disease 2019 Impacts

In March 2020, the Coronavirus Disease 2019 (COVID-19), caused by infection with severe acute respiratory syndrome coronavirus 2, was characterized as a pandemic by the World Health Organization. The COVID-19 pandemic has impacted clinical studies worldwide due to quarantines, site closures, travel limitations, diversion of resources, and/or general interruptions in study-related procedures.

This study protocol includes the guidance for COVID-19 situations, see Section 3.1.4 for details. The impacts of implementing COVID contingency measures on the outcomes of this study, including any protocol deviations that result from COVID-19 illness, will be discussed in the Clinical Study Report.

Treatment with standard of care and/or emergency use authorization medications, including vaccinations and boosters, for COVID-19 **will** be permitted during this study. There is no known negative impact of vaccination on obicetrapib efficacy and safety, nor any known negative impact of obicetrapib on vaccination efficacy and safety.

2 STUDY OBJECTIVES

2.1 Primary Objective

The primary objective of this study is to evaluate the efficacy of objectrapib, compared to placebo, in reducing serum LDL-C measured at Day 56 (Visit 5) when taken as an adjunct to a pre-existing stable statin therapy regime.

2.2 Secondary Objectives

The secondary objectives of this study include the following:

- To evaluate the effect of obicetrapib, compared to placebo, on serum ApoB, non-HDL-C, and HDL-C concentrations at Day 56 (Visit 5), when taken as an adjunct to pre-existing stable statin therapy;
- To assess the mean plasma levels of obicetrapib at steady state on Day 56 (Visit 5) and Day 84 (Visit 6); and
- To evaluate the safety and tolerability profile of obicetrapib in Japanese subjects.

3 STUDY DESCRIPTION

3.1 Summary of Study Design

This study will be a placebo-controlled, double-blind, randomized, Phase 2 dose-finding study to evaluate the efficacy, safety, and tolerability of obicetrapib as an adjunct to stable statin therapy in Japanese participants. This study will take place at approximately 10 sites in Japan.

3.1.1 Screening Period

At the Screening Visit (Visit 1), and up to 2 weeks before the start of the treatment period, participants will be required to sign an informed consent form (ICF) before any study-related procedures are performed. After signing the ICF, participants will be assessed for study eligibility.

3.1.2 Treatment Period

Up to 2 weeks after the Screening Visit, participants will return to the site on Day 1 (Visit 2) and confirm study eligibility before being randomized and beginning treatment. Approximately 100 eligible participants (25 participants per treatment group) will be randomized in a 1:1:1:1 ratio to 1 of the following treatment groups:

- 2.5 mg obicetrapib (one 2.5 mg obicetrapib tablet);
- 5 mg obicetrapib (one 5 mg obicetrapib tablet);
- 10 mg obicetrapib (one 10 mg obicetrapib tablet); or
- Placebo (1 placebo tablet).

During the 8-week Treatment Period, the assigned study drugs will be administered by the participants orally once daily from Day 1 (Visit 2) to Day 56 (Visit 5). Participants will return to the site on Day 14 (Visit 3), Day 28 (Visit 4), and Day 56 (Visit 5) for efficacy, safety, and PK assessments. Participants, Investigators, the Clinical Research Organization (CRO), and the Sponsor will be blinded to all lipid results from Day 1 (Visit 2) for the first participant and continuing to database lock in order to protect blinding to treatment assignment.

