4.5 Withdrawal Criteria

Participation in this study may be discontinued for any of the following reasons:

- The participant withdraws consent or requests discontinuation from the study for any reason;
- Occurrence of any medical condition or circumstance that exposes the participant to substantial risk and/or does not allow the participant to adhere to the requirements of the protocol;
- Any SAE, clinically significant AE, severe laboratory abnormality, intercurrent illness, or other medical condition, which indicates to the Investigator that continued participation is not in the best interest of the participant;
- Pregnancy;
- Requirement of prohibited concomitant medication;
- Participant failure to comply with protocol requirements or study-related procedures; or
- Termination of the study by the Sponsor or the regulatory authority.

Unless the participant withdraws consent, participants who discontinue study drug early should be encouraged to complete the full panel of assessments scheduled for the Early Termination Visit promptly and complete a Safety Follow-up Visit 4 weeks after the last dose. If a participant withdraws prematurely from the study due to the above criteria or any other reason, study staff should make every effort to complete the full panel of assessments scheduled for the Early Termination Visit and complete a Safety Follow-up Visit 4 weeks after the last dose. PK samples will not be collected during the Safety Follow-up Visit for participants who discontinue study drug early without withdrawing consent or for participants who withdraw prematurely from the study. The reason for participant withdrawal must be documented in the electronic case report form (eCRF).

In the case of participant lost to follow-up, attempts to contact the participant must be made and documented in the participant's medical records. Withdrawn participants will not be replaced.

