9.2.5 Sample Size Determination

A sample size of at least 100 evaluable participants (i.e., 25 participants per treatment group) will provide >90% power to detect a 30% difference in LDL-C reduction at Day 56 (SD of 25%) for each of the obicetrapib groups compared to the placebo group at a 2-sided significance level of 0.05.

The sample size for this study was determined in order to provide sufficient power for the analyses of the primary efficacy endpoint described in Section 7. Therefore, assuming a dropout rate of approximately 7%, an estimated enrollment target of approximately 108 participants (i.e., 27 participants per treatment group) is planned for this study. This sample size will also contribute sufficient participant exposure and safety data.

Participants will be stratified according to their Screening Visit (Visit 1) LDL-C levels (≥100 or <100 mg/dL).

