2.2 Study Design

2.2.1 *Overview*

The population for this study includes Japanese men and women, 18 to 75 years of age, inclusive, with a body mass index <35 kg/m², fasting LDL-C levels >70 mg/dL, and triglyceride levels <400 mg/dL at the Screening Visit, who are currently receiving stable statin therapy.

This study will be a placebo-controlled, double-blind, randomized, Phase 2 dose-finding study to evaluate the efficacy, safety, and tolerability of obicetrapib as an adjunct to stable statin therapy in Japanese participants. This study will take place at approximately 10 sites in Japan.

The total duration for the double-blind period for each subject will be up to 14 weeks, including up to 2 weeks for Screening, 8 weeks for blinded study treatment, and 4 weeks for safety follow-up. Please refer to Appendix A (Schedule of Procedures) of the study protocol for details.

At the Screening Visit (Visit 1), and up to 2 weeks before the start of the treatment period, participants will be required to sign an informed consent form (ICF) before any study-related procedures are performed. After signing the ICF, participants will be assessed for study eligibility.

Up to 2 weeks after the Screening Visit, participants will return to the site on Day 1 (Visit 2) and confirm study eligibility before being randomized and beginning treatment. Approximately 100

eligible participants (25 participants per treatment group) will be randomized in a 1:1:1:1 ratio to 1 of the following treatment groups:

- 2.5 mg obicetrapib (one 2.5 mg obicetrapib tablet);
- 5 mg obicetrapib (one 5 mg obicetrapib tablet);
- 10 mg obicetrapib (one 10 mg obicetrapib tablet); or
- Placebo (1 placebo tablet).

During the 8-week Treatment Period, the assigned study drugs will be administered by the participants orally once daily from Day 1 (Visit 2) to Day 56 (Visit 5). Participants will return to the site on Day 14 (Visit 3), Day 28 (Visit 4), and Day 56 (Visit 5) for efficacy, safety, and Pharmacokinetics (PK) assessments. Participants, Investigators, the Clinical Research Organization (CRO), and the Sponsor will be blinded to all lipid results from Day 1 (Visit 2) for the first participant and continuing to database lock in order to protect blinding to treatment assignment.

Participants will return to the site for a Safety Follow-up Visit on Day 84 (Visit 6), approximately 4 weeks after the end of the Treatment Period, for final safety and PK assessments.

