The sample size for this study was determined in order to provide sufficient power for the analyses of the primary efficacy endpoint described in Section 3.4. Therefore, assuming a dropout rate of approximately 7%, an estimated enrollment target of approximately 108 participants (i.e., 27 participants per treatment group) is planned for this study. This sample size will also contribute sufficient participant exposure and safety data.

Participants will be stratified according to their Screening Visit (Visit 1) LDL-C levels (≥ 100 or < 100 mg/dL).

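### The design sections randomise about 100 participants (25 per group), but the sample-size sections need about 108 (27 per group) to leave 100 evaluable

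*Protocol*

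**What the plan says.** **Design text.** Protocol Section 3.1.2 states: "Approximately 100 eligible participants (25 participants per treatment group) will be randomized in a 1:1:1:1 ratio". The Treatment Period paragraph of the synopsis uses the same sentence. SAP Section 2.2.1 gives the same count: "eligible participants (25 participants per treatment group) will be randomized in a 1:1:1:1 ratio".

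**Sample-size text.** Protocol Section 9.2.5 opens with the analysable number, "A sample size of at least 100 evaluable participants (i.e., 25 participants per treatment group", and attaches the power statement to it: more than 90% power for a 30% difference with an SD of 25%, 2-sided 0.05, for each dose against placebo. After allowing for dropout of about 7%, it concludes: "an estimated enrollment target of approximately 108 participants (i.e., 27 participants per treatment group) is planned for this study". The synopsis repeats this, and SAP Section 2.2.4 has the same target: "an estimated enrollment target of approximately 108 participants (i.e., 27 participants per treatment group) is planned".

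**Replacement.** Protocol Section 4.5 says: "Withdrawn participants will not be replaced".

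The SAP's list of changes from the protocol (Section 5) does not mention the number to be randomised.

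**The concern.** The same figure, 25 per group, is the number randomised in one part of each document and the number evaluable in another. With any dropout and no replacement, these are different quantities. The evaluable figure appears to have been carried into the sentence that should give the number randomised. The synopsis holds both versions.

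The number to randomise is a basic design figure. Someone who sets up enrolment from the design section would plan for 8 fewer participants than someone who uses the sample-size section. If the trial randomises 108, it exceeds the number in three design passages. If it randomises 100, it can be expected to fall short of its stated evaluable minimum. Either way, a reader of the final report could ask which number was planned.

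**Working it through.** **Inputs**
- Number randomised by the design text: 100, 25 per group (synopsis; Protocol 3.1.2; SAP 2.2.1).
- Evaluable minimum: 100, 25 per group (synopsis; Protocol 9.2.5; SAP 2.2.4).
- Dropout: about 7%, with no replacement (Protocol 9.2.5 and 4.5).
- Enrolment target: 108, 27 per group (synopsis; Protocol 9.2.5; SAP 2.2.4).
- Power inputs: difference 30, SD 25, 2-sided alpha 0.05.

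**Step 1: reproduce the plan's target.** Number to randomise = evaluable number / (1 − dropout).
- Overall: 100 / 0.93 = 107.5, rounded up to 108.
- Per group: 25 / 0.93 = 26.9, rounded up to 27; 4 × 27 = 108.

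The sample-size section is consistent with itself.

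**Step 2: expected evaluable number under each text.** Evaluable = randomised × (1 − dropout), with every dropout counted as non-evaluable.

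| Text followed | Randomised | Expected evaluable | Per group | Against the minimum of 100 |
|---|---|---|---|---|
| Design sections | 100 | 100 × 0.93 = 93.0 | 23.25 | 7 short |
| Sample-size sections | 108 | 108 × 0.93 = 100.4 | 25.1 | met |

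**Step 3: does the shortfall touch the power claim?** Two-sample t test, noncentrality = 30 / (25 × √(2/n)), degrees of freedom 2n − 2.
- n = 25 per group: 30 / 7.07 = 4.24, 48 df, power 98.6%.
- n = 23 per group: 30 / 7.37 = 4.07, 44 df, power 97.8%.
- n = 16 per group: power 90.7%; n = 15: power 88.7%.

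The claim of more than 90% per comparison therefore needs only about 16 evaluable per group. It holds under either text.

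**The case against.** The strongest reply is that the operative number is stated and correct. Only the sample-size sections are labelled as the sample-size determination, and they give 108. The design paragraphs are narrative summaries, and both figures are introduced as approximate. A reader of either full document will find the planned target. This lowers the weight of the point but does not remove the conflict. The per-group counts are specific (25 against 27), 25 is exactly the evaluable count, and the evaluable figure is a minimum rather than an approximation. Nor can 108 be read as a number screened: it is divided by treatment group, and groups exist only after randomisation.

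A second reply is that 93 is not the number that would enter the primary analysis. This stands. Neither document defines evaluable. The mITT Population needs only one dose and a Baseline LDL-C (SAP 3.2.2), and the primary model uses all available Day 14, 28 and 56 values (SAP 3.4.1). The Early Termination Visit includes a lipid profile (Protocol Appendix A), and one that falls on Days 43 to 70 counts as Week 8 (SAP 3.1.2). Some dropouts would therefore still contribute. The Per-Protocol Population and the two ANCOVA sensitivity analyses do need a Day 56 value, so the completer count is not irrelevant, but it does not describe the primary analysis.

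A reader might also infer more than the documents support:
- *That the trial would be underpowered.* It would not; Step 3 shows a wide margin.
- *That enrolment will stop at 100.* The description of the interactive response system (Protocol 5.3) contains no cap, and no passage tells anyone to stop at 100. The early stop is a possibility if the design text is used, not something the plan directs.
- *That a stated precision is missed.* The documents set no precision target, only a power statement.
- *That 100 randomised can never give 100 evaluable.* It could if nobody became non-evaluable, but that contradicts the plan's own dropout assumption.

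**Conclusion.** The inconsistency is real and occurs in both documents. The design passages give as randomised the number that the sample-size passages require as evaluable; the gap is 8 participants overall and 2 per group. On the plan's own dropout rate, with dropouts counted as non-evaluable, randomising 100 leaves about 93 evaluable, while randomising 108 leaves 100.4. The 93 rests on both of those assumptions and is not a forecast of the primary analysis set.

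The consequence is limited to the enrolment figure and the evaluable minimum. Power per comparison would be about 98% either way, and the analysis and the error rate are untouched. This is a correction of internal consistency in a number that the trial relies on. It is not a challenge to the adequacy of the design.

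**What to change.** In the Treatment Period paragraph of the synopsis, in Protocol Section 3.1.2 and in SAP Section 2.2.1, state that approximately 108 participants (27 per treatment group) will be randomised. Keep 100 (25 per group) only in the sample-size text, as the evaluable number. Protocol Section 9.2.5 and SAP Section 2.2.4 need no change.

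The cost is wording in three places, with the protocol edits going through the amendment process in Protocol Section 12.1. No participants are added beyond the 108 already planned, and no analysis changes.
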